Neural Basis of the Effect of EMDR Therapy

Study Protocol and Statistical Analysis Plan

26/11/2023

Participants

Using the G*Power 3.1.9.7 software (Faul et al., 2009), an a priori power analysis was conducted to determine the required sample size. The analysis was based on a mixed-design ANOVA framework, consistent with the primary hypothesis testing the interaction between Group (experimental vs. control) and Time (pre- vs. post-stimulation). As no previous ERP studies had specifically examined the effects of Butterfly Tapping on LPP modulation, the expected effect size was set to a conventional medium value (Cohen's $f=0.25$), following Cohen's guidelines (Cohen, 1988). The significance level (α) was set at 0.05, and statistical power ($1-\beta$) was set to 0.95. Under these assumptions, the estimated minimal sample size was 36 participants. To account for potential data loss due to EEG artifacts or technical issues, a total of 38 university students and staff were initially recruited.

This power estimation represents a conservative approximation of the effective statistical sensitivity of the study, as it does not explicitly model features known to enhance power in ERP research, including the repeated-measures structure, the use of differential waveforms (negative minus neutral), and the averaging of a large number of trials across spatially defined electrode clusters. From a sensitivity perspective, the final sample size can therefore be considered sufficient to detect Group \times Time interaction effects of small-to-medium magnitude, which is consistent with effect sizes typically reported in studies examining LPP modulation during emotion regulation and affective interventions. Consequently, the study was adequately powered to address its primary neurophysiological hypotheses.

Participants were healthy, aged between 18 and 40 years (mean age = 25.1 years; SD = 3.0) (55% of females) with normal or corrected-to-normal vision. Inclusion criteria required full right-handedness as self-reported (Edinburgh Handedness Inventory; Oldfield, 1971), no history of neurological or psychiatric disorders, and no current use of psychoactive medications. All participants were naïve to the purpose of the study. Data was collected between July 2024 and February 2025. Participants were pseudo-randomly assigned to the experimental (Exp) or control (Con) group, which were balanced for sex and age.

Self-Report Measures

To verify the comparability of the two groups, participants completed the trait sub-scale of the State-Trait Anxiety Inventory (STAI-Y2; Spielberger et al., 1971) at the beginning of the experimental session. This 20-item self-report questionnaire evaluates stable personality-related tendencies to experience anxiety across time and situations. Independent samples t-tests confirmed no significant differences between groups ($t < 1$).

To capture transient emotional responses associated with the experimental manipulation, participants completed two tests, the State subscale of the STAI (STAI-Y1; Spielberger et al., 1971) and the Visual Analogue Scale (VAS; Gift, 1989), immediately after the Tasks described below. Specifically, the STAI-Y1 consists of 20 items assessing how anxious the participant feels "at the moment", rated on a 4-point Likert scale ranging from 1 ("not at all") to 4 ("very much so"). It provides a reliable index of momentary anxiety and is sensitive to situational changes, making it well-suited to evaluating the

effects of affective processing interventions. Furthermore, the VAS was used to quantify subjective emotional discomfort related to the negative emotional content of the task. Participants were asked to indicate the intensity of discomfort experienced while viewing the negative images, with endpoints labeled “no discomfort” (0) and “extreme discomfort” (100). The VAS is a well-validated tool for capturing subtle affective changes in a fast and intuitive manner and is particularly useful in protocols involving repeated measures.

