
modulation of interest. The electrodes included in the analysis were selected according to the scalp distribution of maximal amplitude in this window, averaging all sites whose activity exceeded 80% of the GFP peak. This procedure identified two electrode pools: a frontal cluster including F1, Fz, F2, FC1, FCz, and FC2, and a centro-parietal cluster comprising Cz, C1, C2, CP1, CPz, and CP2, both consistent with the canonical distribution of the LPP component (Hajcak et al., 2010). Mean amplitudes in this time window and pool were extracted for each condition and used in subsequent statistical comparisons.

Statistical Analysis

Prior to statistical testing, the normality assumption for all variables was assessed using the Shapiro–Wilk test. None of the distributions deviated significantly from normality. The assumption of homogeneity of variance was tested using Levene’s test, which confirmed that the data met the criterion for homoscedasticity. The behavioral and psychological measures were analyzed using a 2×2×2 ANOVA, with Group (Exp vs. Con) as a between-subjects factor and Time (T0 vs. T1) and Valence (Negative vs. Neutral) as a within-subjects factor. Furthermore, a 2×2 ANOVA was conducted on the mean amplitudes of the Frontal Positivity and cLPP difference waves, with Group and Time as factors. Effect sizes were reported using partial eta squared (η^2). Where significant main effects or interactions were found, Bonferroni-corrected post-hoc tests were applied. All tests adopted an α threshold of 0.05. Analyses were performed using Statsoft Statistica 12.0 (StatSoft Inc., Tulsa, OK, USA).

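### The 36 participants stated for 95% power do not follow from the stated inputs; for the 2×2 Group × Time test they suffice only if the T0–T1 correlation is about 0.67 or more

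*Combined protocol and SAP*

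**What the plan says.** The Participants section reports an a priori G*Power calculation for a mixed-design ANOVA, tied to the primary hypothesis "testing the interaction between Group (experimental vs. control) and Time (pre- vs. post-stimulation"). The inputs given are f = 0.25, chosen as a conventional medium value because no earlier ERP study of this tapping technique was available, α = 0.05 and power 0.95. The result: "Under these assumptions, the estimated minimal sample size was 36 participants". To allow for data loss, 38 were recruited.

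The next paragraph calls this estimate conservative. Its reason is that the calculation did not explicitly model the repeated-measures structure, the difference waveforms or the averaging over many trials. It then infers that the sample can detect small-to-medium interactions and that power for the primary hypotheses was adequate.

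The Statistical Analysis section defines the ERP test: "a 2×2 ANOVA was conducted on the mean amplitudes of the Frontal Positivity and cLPP difference waves, with Group and Time as factors". A separate 2×2×2 ANOVA, with "Time (T0 vs. T1) and Valence (Negative vs. Neutral) as a within-subjects factor", is used for the behavioral and psychological measures.

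**The concern.** For a within-between interaction, the required N depends on the number of measurements per participant (m) and on the correlation between them (r), as well as on f, α and power. The plan gives neither m nor r, so 36 cannot be derived from what is written.

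The Statistical Analysis section does settle m for the ERP test. Subtracting neutral from negative removes Valence, which leaves one value at T0 and one at T1, so m = 2. With two measurements and a moderate correlation, 36 is well short of what 95% power requires.

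At stake is how the primary result is read. The section moves from this figure to claims about sensitivity and adequacy. If the true type II error at f = 0.25 is 15–17% or more, and not 5%, a non-significant Group × Time interaction is weaker evidence of no effect than the text implies.

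**Working it through.** **Inputs from the documents.** Two groups (k = 2); two time points on difference waves (m = 2); f = 0.25, so f² = 0.0625; α = 0.05; target power 0.95; N = 36 stated and 38 recruited.

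**Assumptions, because the documents are silent.** Equal groups, sphericity, and r, for which a range is shown.

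**Formula.** Noncentral F for the within-between interaction:
- λ = N·f²·m/(1 − r)
- df1 = (k − 1)(m − 1)
- df2 = (N − k)(m − 1)

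**Step 1: reproduce 36.** With m = 4 and r = 0.5, λ = 36 × 0.0625 × 4/0.5 = 18, df = 3 and 102, power 0.952. At N = 34 power is 0.939, so 36 is the minimum for that setting. Four measurements would correspond to Time × Valence cells, but the plan tests no 3-df Group interaction.

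**Step 2: the planned test.** With m = 2 and r = 0.5:
- N = 36: λ = 36 × 0.0625 × 2/0.5 = 9.0, df = 1 and 34, power 0.830.
- N = 38: λ = 9.5, df = 1 and 36, power 0.851.
- N = 52: λ = 13.0, power 0.942.
- N = 54: λ = 13.5, power 0.950, so 54 is the minimum.

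Cross-check: with two time points this is a t test on change scores. An f of 0.25 means a difference in mean change of 4 × 0.25 = 1.0 SD. The SD of change is √(2(1 − 0.5)) = 1, so d = 1.0. The exact t test needs 27 per group (54 in all) and gives 0.830 with 18 per group and 0.851 with 19.

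**Step 3: dependence on r (m = 2, f = 0.25).**

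| r | N for 95% | Power at 36 | Power at 38 |
|---|---|---|---|
| 0 | 106 | 0.54 | 0.56 |
| 0.3 | 76 | 0.69 | 0.72 |
| 0.5 | 54 | 0.83 | 0.85 |
| 0.6 | 44 | 0.90 | 0.92 |
| 0.7 | 34 | 0.96 | 0.97 |
| 0.8 | 24 | >0.99 | >0.99 |

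Power reaches 0.95 at r ≈ 0.673 for N = 36 and at r ≈ 0.654 for N = 38.

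**Step 4: is 36 conservative?** If the repeated-measures gain is left out (λ = N·f², 1 and N − 2 df), 95% power needs 210: λ = 210 × 0.0625 = 13.125, power 0.950. Even counting both measurements but taking r = 0, 106 are needed. The figure 36 therefore already contains a large repeated-measures gain, and that gain cannot be held back as a reserve.

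**Step 5: smaller effects (m = 2, r = 0.5, N = 38).** Power is 0.67 at f = 0.20, 0.44 at f = 0.15 and 0.22 at f = 0.10. The effect detectable with 80% power is f = 0.23, close to the medium value itself.

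**The case against.** The strongest reply is that r is unknown. The 54 and the 83–85% belong to r = 0.5, which the documents do not state. If the difference-wave amplitudes correlate at 0.67 or more between T0 and T1, 36 is enough. The design does not settle the matter: many trials per condition within one session favour a high correlation, while different image sets at T0 and T1 may lower it. This stands. A reader might infer that 36 is simply wrong and 54 right, but the documents do not support that without an assumed r.

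A reader might also infer from the exact match in Step 1 that four measurements were entered by mistake. The match is suggestive, and the plan does have a four-cell Time × Valence layout for other measures. But no software settings are reported, and two measurements with r near 0.68 also give 36.

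Third, data collection ended in February 2025, no test or dataset changes, and 83–85% power at f = 0.25 is respectable by ordinary standards. This also stands, and the point does not show the study to be unsound. It limits the remedy to the power statement.

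What the reply does not rescue is the text as written. It claims 95% power from inputs that do not determine N. It also cannot rely on an undisclosed high correlation while saying that the repeated-measures structure was not explicitly modelled.

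**Conclusion.** The concern holds in conditional form. The stated minimum of 36 for 95% power does not follow from the stated inputs. For the 1-df test that the plan runs, it is correct only if r is about 0.67 or more, a value that is neither stated nor justified. At r = 0.5 the shortfall is 54 − 36 = 18 participants against the stated target, and the type II error is 17% at 36 and 15% at 38, against the stated 5%. At r = 0.3 it is 31% and 28%; at r = 0.7 it is 4% and 3%. The description of the estimate as conservative is incompatible with 36 unless further unstated inputs are supplied. Sensitivity to small-to-medium interactions is not supported at r = 0.5. These results assume equal groups, and those for 38 assume that all recruited participants were analysed; the documents give neither the group sizes nor the number analysed.

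**What to change.** Correct the Participants section, without enrolling more:

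1. State that the calculation is for the 1-df Group × Time interaction on the difference waves, with two groups and two measurements. State the assumed r and its justification.
2. Replace 36 as the minimum for 95% power with the N recomputed under that r (for example, 54 at r = 0.5).
3. Report power at the design value f = 0.25, for the number and group sizes actually analysed, over a range of r. If all 38 were analysed in equal groups, this is 72%, 85% and 97% at r = 0.3, 0.5 and 0.7.
4. Remove the claim that the estimate is conservative. Remove or qualify the statements on small-to-medium sensitivity and adequate power so that they agree with the recomputed figures.

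The cost is a few sentences and no change to any analysis. The downside is that the stated power becomes less favourable unless a high correlation can be justified.

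### The power estimate is called conservative for omitting repeated measures that N = 36 already counts, and sensitivity below f = 0.25 is not demonstrated

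*Combined protocol and SAP*

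**What the plan says.** All the power text is in the Participants section of the combined protocol and SAP. Its first paragraph describes the calculation: "The analysis was based on a mixed-design ANOVA framework", aimed at the Group × Time interaction. On the effect size, "the expected effect size was set to a conventional medium value", namely f = 0.25. "The significance level (α) was set at 0.05", and power "was set to 0.95". The result: "the estimated minimal sample size was 36 participants". Thirty-eight people were recruited.

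The second paragraph then says: "This power estimation represents a conservative approximation of the effective statistical sensitivity of the study, as it does not explicitly model features". It lists three features: the repeated-measures structure, the negative-minus-neutral difference waveforms, and averaging over many trials within electrode clusters. It infers that the final sample suffices for "interaction effects of small-to-medium magnitude" and concludes that power was adequate for the primary neurophysiological hypotheses.

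The section does not give the correlation between T0 and T1, the number of measurements entered in G*Power, the group sizes, the number analysed or any sensitivity calculation. The Statistical Analysis section confirms that the ERP test is a 2×2 Group by Time ANOVA on difference-wave mean amplitudes.

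**The concern.** The two paragraphs cannot both be right. A mixed-design ANOVA calculation for Group × Time is a repeated-measures calculation, so the repeated-measures structure cannot also be an unused reserve that makes the result conservative. The sensitivity statement rests on that supposed reserve and has no calculation behind it.

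At stake is how the Group × Time results are read. If readers accept that 38 people suffice for effects below f = 0.25, a non-significant interaction looks like evidence against such effects. They would also have no reason to ask which correlation the sample size depends on.

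**Working it through.** **Inputs.** From the Participants section: f = 0.25, α = 0.05, power 0.95, two groups, two times, N = 36 required, 38 recruited. Assumed: equal groups; all 38 analysed; r varied, because the plan gives none.

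**Formulas.** For a within-between interaction with k = 2 groups and m measurements, the noncentral F has λ = N f² m/(1 − r), with df (m − 1) and (N − 2)(m − 1). For m = 2 this is the two-sample test on T1 − T0 change, with λ = N d²/4. Here d is the group difference in change divided by the SD of the change score, so d = f·√(8/(1 − r)).

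**1. Reproducing N = 36.** For f = 0.25 and 95% power:

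| Setting | N needed | Power at N = 36 |
|---|---|---|
| Between-subjects, one measurement (λ = N f²) | 210 | 31% |
| Stated interaction, m = 2, r = 0 | 106 | 54% |
| Stated interaction, m = 2, r = 0.5 | 54 | 83% |
| Stated interaction, m = 2, r = 0.68 | 36 | 95% |
| m = 4, r = 0.5 | 36 | 95% |

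As an example, m = 2 and r = 0.5 at N = 36 gives λ = 36 × 0.0625 × 2/0.5 = 9.0 on (1, 34) df, hence 83%. N = 38 gives λ = 9.5 and 85%.

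With two measurements, 36 arises only for r between about 0.67 and 0.69. With four measurements it arises at r = 0.5, but that is a 3-df interaction and not the Group × Time test described. For the stated test, 36 cannot be reached without crediting within-person correlation.

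**2. The other two features.** The analysed outcome is already the difference-wave amplitude, and trial averaging determines the SD of that outcome. Cohen's f is standardised to that SD. Once f is fixed at 0.25, neither feature adds power. They could justify expecting a larger f, but the plan does not argue this.

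**3. Sensitivity at N = 38.** Solving for d on (1, 36) df gives 0.93 at 80% power and 1.20 at 95%. These are SDs of the change score and do not depend on r. Converting with f = d·√((1 − r)/8):

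| r | f at 80% power | f at 95% power | Power at f = 0.10 | Power at f = 0.175 |
|---|---|---|---|---|
| 0.5 | 0.23 | 0.30 | 22% | 56% |
| 0.68 | 0.19 | 0.24 | 32% | 75% |
| 0.8 | 0.15 | 0.19 | 48% | 91% |
| 0.9 | 0.10 | 0.13 | 77% | >99% |

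The value 0.175 is the midpoint of 0.10 (small) and 0.25 (medium). The r = 0.68 row is the one that makes the plan's own 36 correct for its stated test. There, 38 people lower the f detectable at 95% power only from 0.25 to 0.24.

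For a difference in change of half a change-score SD, λ = 38 × 0.25/4 = 2.375 and power is 32%.

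If 36 are analysed instead of 38, the detectable d is 0.96 at 80% power and 1.24 at 95%.

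**The case against.** The strongest reply is that the sensitivity verdict turns on a correlation the documents do not give. That stands. At r = 0.8 the test has 91% power for f = 0.175, and at r = 0.9 the 80%-power f is 0.10. A reader might infer that the small-to-medium claim is false; the documents support only that it is undemonstrated.

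A reader might also infer that 38 people can detect only differences of about one SD. That holds in SDs of the change score. In SDs of the raw amplitude, the 80%-power difference is 0.934 × √(2(1 − r)): 0.93 at r = 0.5 but 0.59 at r = 0.8. The two scales coincide only at r = 0.5.

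Nor can one say without qualification that the study is unable to rule out a half-SD difference. With 19 per group the 95% CI half-width is 2.028 × √(2/19) = 0.66 change-score SD. At r = 0.8 that is 0.66 × √0.4 = 0.42 raw SD, so an interval centred on zero would exclude half a raw SD.

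Three smaller replies have merit. The N = 210 comparator removes the second measurement as well as the correlation, so 106 is the fairer contrast; it is still about three times 36. Calling f = 0.25 medium follows the cited convention and is not an error. Data collection is over, and the plan nowhere says that a null result excludes small effects, so that harm concerns interpretation and is not something the text asserts.

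None of this rescues the reasoning. The double counting holds at any r.

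**Conclusion.** The description of the estimate as conservative is wrong as written: the repeated-measures gain is already in N = 36, and the other two features add nothing at a fixed f. At an assumed r = 0.5 the estimate for the stated test is optimistic, with 83% power at N = 36 against the 95% claimed, and 54 needed.

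The claim of sensitivity below a medium effect is not demonstrated, and the adequacy conclusion drawn from it falls with it. It would need a high r that the plan neither states nor justifies. The change-score figures of 0.93 and 1.20 SD rest on 38 analysed in equal groups; the f figures rest additionally on r. The documents do not show which settings were entered in G*Power, so whether 36 came from an r near 0.68, from four measurements or from something else remains open.

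**What to change.** In the Participants section:

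- Delete the sentences calling the estimate conservative and claiming small-to-medium sensitivity, and the conclusion of adequate power drawn from them.
- State the r and the number of measurements entered in G*Power. If they do not match the two-group, two-time interaction, say so.
- Add a sensitivity statement for the number actually analysed in each group. For 19 per group it could read: at two-sided α = 0.05 the Group × Time test has 80% power for a group difference in change of 0.93 SD of the change score and 95% power for 1.20 SD; in f units these are 0.23 and 0.30 at r = 0.5, 0.19 and 0.24 at r = 0.68, and 0.15 and 0.19 at r = 0.8.

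In the Statistical Analysis section, add the 95% CI of the Group × Time difference for each outcome, and note that a non-significant result does not by itself exclude smaller effects.

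The cost is one rewritten paragraph and one interval per outcome. No new data are needed and the planned tests do not change. The stated sensitivity becomes less favourable.

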2.3. Stimuli

A total of 240 images were selected from the Nencki Affective Picture System (NAPS; Marchewka et al., 2014), a standardized database widely used for emotion research. Specifically, this database includes realistic photographs categorized by five content types: people, faces, animals, objects, and landscapes, each rated along three affective dimensions: valence (from 1 = very negative to 9 = very positive), arousal (from 1 = very calm to 9 = highly arousing), and approach/avoidance motivation (from 1 = strong tendency to avoid to 9 = strong tendency to approach).

In the present study, the images used were divided into two emotional categories (negative and neutral), and each category was presented across two separate tasks (Task 1 and Task 2). Each task included 60 images of the same emotional valence, resulting in 60 negative images in Task 1, 60 negative images in Task 2, 60 neutral images in Task 1, and 60 neutral images in Task 2. Importantly, the image sets used in Task 1 and Task 2 were not repeated across time points. Specifically, each participant viewed one set at T0 and the other at T1, with the set assignment randomized across participants. This design allowed us to evaluate the generalizability of any observed effects to novel, previously unseen stimuli. All images were selected based on normative valence ratings, approach–avoidance motivation, and arousal, ensuring internal consistency within emotional categories (see Table 1).

Table 1. Mean ratings of valence, avoidance/approach motivation (Av/Ap), and arousal of the 240 images included in the tasks.

	Valence	Av/Ap	Arousal
Negative – Task 1	2.57	2.86	6.86
Negative – Task 2	2.66	2.87	6.73
Neutral – Task 1	5.53	5.49	4.67
Neutral – Task 2	5.54	5.44	4.72

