2.4. Task

Participants were comfortably seated in a dimly lit room, approximately 100 cm from a 32” 16:9 computer monitor. Visual stimuli were presented using Presentation Software (Neurobehavioral Systems, Albany, CA, USA). A small yellow fixation point (0.15×0.15° of visual angle) on a grey background remained visible at the center of the screen throughout the experiment to maintain gaze stability and minimize ocular artifacts. The experimental task was a variant of a simple detection task, where the participant had to respond as soon as possible to the visual stimuli described above using a response key with their right index finger, regardless of their emotional content.

In each trial, images were presented in full-screen mode (subtending 35.4 x 31.7°) at the center of the display for 350 ms, then the fixation point remained for a randomized inter-stimulus interval ranging from 1200 to 3000 ms. The task was structured into 12 consecutive runs, alternating in emotional valence: 6 runs of negative images and 6 runs of neutral images. Each run contained 60 images of the

same valence. The order of runs (starting with neutral or negative) was counterbalanced across participants to control for sequence effects. Each run lasted about 2 min and 30 sec, resulting in a recording session duration of approximately 35 min, including breaks. For each valence, 360 trials were collected, for a total of 720 trials per participant. This task has been executed during EEG recordings before and after the stimulation session described below.

Stimulation

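### Picture set is confounded with Time within each participant, yet the Group × Time models omit set order and its balance between groups is not documented

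*Combined protocol and SAP*

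**What the plan says.** Section 2.3 (Stimuli) describes two non-overlapping picture sets, the Task 1 and Task 2 sets, each with 60 negative and 60 neutral images. Of their use it says that "each participant viewed one set at T0 and the other at T1, with the set assignment randomized across participants". On matching it says: "All images were selected based on normative valence ratings, approach–avoidance motivation, and arousal, ensuring internal consistency within emotional categories". Table 1 gives mean ratings by set.

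Two other design factors were controlled. Section 2.4 (Task) says: "The order of runs (starting with neutral or negative) was counterbalanced across participants to control for sequence effects". The Participants section says: "Participants were pseudo-randomly assigned to the experimental (Exp) or control (Con) group, which were balanced for sex and age".

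The Statistical Analysis section carries none of these into the models. For the ERP outcomes, "a 2×2 ANOVA was conducted on the mean amplitudes of the Frontal Positivity and cLPP difference waves, with Group and Time as factors". The behavioural and psychological measures get a three-factor ANOVA, "with Group (Exp vs. Con) as a between-subjects factor and Time (T0 vs. T1) and Valence (Negative vs. Neutral) as a within-subjects factor".

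The documents do not say that set order was balanced within group, give no counts of order by group, and do not say whether a participant's run order was the same at T0 and T1.

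**The concern.** The primary hypothesis is the Group × Time interaction. In a 2×2 mixed ANOVA that test compares the T1−T0 change between groups. Because the sets swap between sessions, a participant who sees the Task 1 set first has a change containing (Task 2 set − Task 1 set). One who sees the Task 2 set first has the opposite sign.

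Any difference between the sets in the negative-minus-neutral response then acts in two ways:

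- If the orders are unevenly split between groups, part of the set difference appears in the Group × Time estimate.
- If they are evenly split, the set difference stays in the error term as scatter that the design could have removed.

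More trials do not help. Section 2.4 gives 360 trials per valence per session and section 2.3 gives 60 images per valence per set, so each image is shown about 360/60 = 6 times. The set difference rests on the same 60 pictures throughout.

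**Working it through.** **Inputs from the documents.** 38 recruited, f = 0.25 (Participants); α of 0.05 (Statistical Analysis); Table 1 ratings.

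**Assumptions.** 19 per group (group sizes are not given). SD of change within an order = 1. Set order shifts the change by +δ or −δ; the documents give no δ, so the range 0 to 0.75 is shown. Correlation between T0 and T1 of 0.5 (not stated).

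**1. How different are the sets?** The plan states no set effect. Its nearest figures are the negative-minus-neutral gaps in Table 1:

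| Rating | Task 1 | Task 2 | Difference in size |
|---|---|---|---|
| Arousal | 6.86−4.67 = 2.19 | 6.73−4.72 = 2.01 | 0.18 |
| Valence | 2.57−5.53 = −2.96 | 2.66−5.54 = −2.88 | 0.08 |
| Av/Ap | 2.86−5.49 = −2.63 | 2.87−5.44 = −2.57 | 0.06 |

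The largest, arousal, is 0.18/2.10, about 9% of the mean contrast.

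**2. Chance imbalance.** Let X and Y be the numbers in each group seeing the Task 1 set first, each Bin(19, 0.5). Then X−Y+19 is Bin(38, 0.5), and P(|X−Y| ≥ 4) = 2·P(Bin(38, 0.5) ≤ 15) = 0.256. For 5 or more it is 0.143; for 6 or more, 0.073. If order was instead fixed at 19 and 19 overall but not within group, the probability of 4 or more is 0.19.

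**3. Shift in the estimate.** Shift = 2δ(pE − pC), where pE and pC are the shares of each group with a given order. For 12/19 v 7/19, pE − pC = 5/19 = 0.263, so at δ = 0.25 the shift is 2 × 0.25 × 0.263 = 0.13 SD of change. Averaged over independent randomisations the shift is zero.

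**4. Variance.** With orders about evenly split, the residual variance of change is multiplied by 1+δ², and its SD by √(1+δ²).

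**5. Simulation of change scores** (19 v 19, 40,000 replicates). The true effect is 1 SD of change: f = 0.25 in a 2×2 interaction is a difference in changes of 4 × 0.25 = 1 within-cell SD, and at correlation 0.5 the SD of change is √(2 × 0.5) = 1 within-cell SD. As a check, the noncentral-F calculation at N = 38 gives power 0.851, against 0.849 simulated at δ = 0. (The plan's N of 36 is reproduced by that formula with four repeated measurements, power 0.952, and not with two, where 54 are needed. That is a separate matter.)

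| δ | Variance factor | Power without term | Power with term | Shift at 12/19 v 7/19 | Type I error there, no term | Type I error at 10/9 v 9/10, no term |
|---|---|---|---|---|---|---|
| 0 | 1.00 | 0.849 | 0.838 | 0 | 0.050 | 0.050 |
| 0.1 | 1.01 | 0.845 | 0.838 | 0.05 | 0.051 | 0.049 |
| 0.25 | 1.06 | 0.826 | 0.838 | 0.13 | 0.059 | 0.044 |
| 0.5 | 1.25 | 0.763 | 0.838 | 0.26 | 0.083 | 0.031 |
| 0.75 | 1.56 | 0.665 | 0.838 | 0.39 | 0.105 | 0.017 |

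The power columns, and an overall type I error of 0.05 (0.049 at δ = 0.75 without the term), are for order randomised independently of group. With the term, type I error is 0.050 to 0.051 in every scenario.

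**The case against.** The strongest reply has four parts.

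*Randomisation already deals with it.* A reader might infer that the plan builds a systematic bias into Group × Time, or that its standard errors are simply too large. The documents support neither. If order was randomised independently of group, the expected bias is zero, type I error is 0.05, and the usual standard error already includes the chance imbalance. The test is conservative only if order was balanced within group, and then little leaks: 0.01 to 0.08 SD for δ of 0.1 to 0.75. This stands. What remains is possible imbalance in this trial and lost precision.

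*The sets are well matched.* If the ERP difference scaled with the arousal gap (an assumption), δ = 0.25 would need a mean negative-minus-neutral effect of 0.25/(0.18/2.10) = 2.9 SDs of change, and δ = 0.5 would need 5.8. That argues for a small δ. It does not settle the matter, because Table 1 covers mean affective ratings only, and matching of content type or physical image properties between sets is not reported.

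*The other design factors are different.* A reader might infer that leaving out sex and age makes the standard errors too large. For the planned contrast it does not follow: their main effects cancel in T1−T0, and they matter only if they modify the change. Starting valence cancels too if each participant kept the same run order at both sessions. A simulation with 20,000 replicates, in which sex, age and starting valence do not affect the change, shows the price of adjusting for everything at δ = 0: power falls from 0.848 to 0.824 with set order, sex and age, and to 0.812 with starting valence as well.

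*It would be post hoc.* Data collection has ended, so replacing the main model now has its own cost. This also stands, and it determines where the extra analysis belongs.

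**Conclusion.** The point holds for set order. It is confounded with Time within each participant, it is absent from every Group × Time model, and its balance between groups is undocumented. This is not a systematic bias, and the planned test is not invalid.

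The size depends on two unknowns, the actual split of order by group and δ. With 19 per group and simple randomisation, a difference of 4 or more people has a 26% chance. A 12/19 v 7/19 split shifts the estimate by 0.13 SD at δ = 0.25 and 0.26 SD at δ = 0.5. At δ of 0.1 or less the adjustment gains nothing; from about 0.25 it starts to pay, and at δ = 0.5 it recovers about 7 points of power (0.763 to 0.838). The worst case for including the term under independent randomisation is a loss of about 1 point (0.849 to 0.838).

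That balance favours adding set order as a low-cost improvement. It does not favour adding sex, age and starting valence as a matter of course.

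**What to change.** - Tabulate set order and starting valence by group, and state whether each participant's run order was the same at T0 and T1.
- Add set order (Task 1 set first v. Task 2 set first) as a between-subject term, with its interaction with Time, to the Group × Time analyses of the Frontal Positivity and cLPP difference waves, STAI-Y1 and VAS. An equivalent form is to regress T1−T0 on Group and set order.
- Because the data are already collected, report this beside the planned ANOVA, labelled as added, and show both estimates with their intervals.
- Add starting valence for STAI-Y1 only if run order differed between sessions. With 12 alternating runs, a neutral start means a negative last run just before that scale. The VAS asks specifically about the negative images, so that argument does not carry over to it.
- Treat sex and age as a secondary sensitivity analysis at most.

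Cost: a paragraph in the SAP and a re-run on data already held. One residual degree of freedom is used (38−2 = 36 becomes 35), or about 1 point of power if the sets do not differ.
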